## 1. PREVIOUS STUDY HISTORY

Has this study ever been reviewed and rejected/disapproved by another IRB prior to submission to this IRB?

No  Yes – if yes, please explain: |

## 2. BRIEF SUMMARY OF RESEARCH

- *The summary should be written in language intelligible to a moderately educated, non-scientific layperson.*
- *It should contain a clear statement of the rationale and hypothesis of your study, a concise description of the methodology, with an emphasis on what will happen to the subjects, and a discussion of the results.*
- *This section should be ½ page*

Over half of Hispanic/Latino (H/L) patients will develop types 2 diabetes (T2D) during their lifetime. According to the Center of Disease Control (CDC), T2D is a leading cause of suffering and death due to cardiovascular disease, end-stage renal failure, blindness, non-traumatic lower limb amputations, hospitalizations, and poor QoL. The risk of dying for people with T2D is twice that of those without T2D. In the US, the prevalence in H/L males 65-74 is 31.1%; for H/L females, it is 32.6%. Compared to non-H/L whites, the risk of diagnosed T2D is 66% higher among H/L. The National Academy of Medicine (NAM) indicates that H/L experience a 50–100% higher illness burden and mortality from T2D than non-H/L whites and that T2D remains poorly managed. The literature unequivocally shows that racial/ethnic minorities with T2D have poor access to healthcare and lower levels of T2D management.

Diabetes Telehealth Management (DTM) improves important outcomes, such as glycemic management (GM) and quality of life (QoL). It is yet unknown whether these results generalize to Hispanic/Latino (H/L) disadvantaged populations with Type 2 Diabetes (T2D), primarily when utilizing community-based participatory research (CBPR) approaches involving patients, caregivers, providers and other stakeholders in the process of adapting the intervention. The

proposed research has great potential to enhance evidence quality, empowering disadvantaged patients with T2D to make informed health decisions and improve outcomes. The study is designed to iteratively tailor DTM to the specific needs of the H/L patients, caregivers, and providers. It addresses several access issues consistently identified in disparities research and has the potential to improve adherence through increased engagement. Our goal is to compare DTM to comprehensive outpatient management (COM) on critical patient-centered outcomes. Both are based on 2018 American Diabetes Association (ADA) guidelines. We propose a multiphase mixed method, CER RCT to:

**Specific Aim 1: Assess usability of an evidence-based DTM intervention utilizing a CBPR approach and adapt it to facilitate acceptability and feasibility in a population of H/L patients with T2D, and their caregivers and providers.**

**Specific Aim 2: Assess whether H/L patients receiving DTM attain significantly *improved* patient-centered outcomes compared to COM, through a CER RCT. *Expected outcomes* include *improved* diabetes QoL, GM, blood pressure (BP), cholesterol, medication adherence, and diabetes self-efficacy (SE), and *reduced* diabetes distress, problem areas in diabetes (PAID), inpatient utilization, unscheduled T2D physician visits and sick days.**

### 3. INTRODUCTION/BACKGROUND MATERIAL/PRELIMINARY STUDIES AND SIGNIFICANCE

- *Describe and provide the results of previous work by yourself or others, including animal studies, laboratory studies, pilot studies, pre-clinical and/or clinical studies involving the compound or device to be studied.*
- *Include information as to why you are conducting the study and how the study differs from what has been previously researched, including what the knowledge gaps are.*
- *Describe the importance of the knowledge expected to result*

Over half of Hispanic/Latino (H/L) patients will develop types 2 diabetes (T2D) during their lifetime. According to the Center of Disease Control (CDC), T2D is a leading cause of suffering and death due to cardiovascular disease, end-stage renal failure, blindness, non-traumatic lower limb amputations, hospitalizations, and poor QoL. The risk of dying for people with T2D is twice that of those without T2D. In the US, the prevalence in H/L males 65-74 is 31.1%; for H/L females, it is 32.6%. Compared to non-H/L whites, the risk of diagnosed T2D is 66% higher among H/L. The National Academy of Medicine (NAM) indicates that H/L experience a 50–100% higher illness burden and mortality from T2D than non-H/L whites and that T2D remains poorly managed. H/L patients with T2D have renal insufficiency rates 3 to 6 times greater than those of non-H/L white patients and

end-stage renal disease rates are 41% higher. For H/L, the prevalence of diabetic retinopathy is 84% higher than that of non-H/L whites. Compared to non-H/L whites, H/L Americans bear twice the risk of lower extremity amputation. The literature unequivocally shows that racial/ethnic minorities with T2D have poor access to healthcare and lower levels of T2D management.

Two 2016 systematic reviews, one based on 111 RCTs and another on 55 RCTs, both showed that DTM significantly improves GM; however, less than 25% of RCTs were conducted with ethnically diverse patients, which diminishes the external validity of the findings. Polisen et al.'s meta-analysis of 26 studies also showed a positive effect on GM, noting that more research of higher methodological quality is required, and recommends including patients from diverse backgrounds to increase external validity and assess technology adaptation to optimize use among different populations. Another meta-analysis which concluded that DTM improves GM, notes that studies *should utilize CBPR approaches* involving patients and caregivers to develop personalized interventions to enhance persistence in usage and treatment adherence. Similarly, a 2017 overview of systematic reviews of mHealth T2D interventions found that they significantly reduce HbA1c when compared to COM. However, few studies have examined mHealth technologies in patients from disparity populations or specifically tailored them to fit the cultural, linguistic, and other needs of underserved groups. DTM programs have shown promise in improving GM in disparity populations. The ADA recommends patient-centered management strategies for T2D, but there has been no effort to date to specifically tailor a comprehensive, evidence-based DTM program to meet the needs of patients from H/L disparity populations. Interventions based on models that involve cultural, personal, caregiver and community factors and tailor care to patient preferences have been shown to have a higher probability of success. Our research is germane to the NAM priority topics for CER, which recommends CER by comparing DTM and COM in managing chronic disease and enhancing medication adherence. Although effective in the general population, we do not know how DTM should be tailored to the needs of H/L disparity patients. Our study seeks to fill critical knowledge gaps identified by meta-analyses, systematic reviews and the NAM, by directly comparing DTM to COM, an existing best practice based on 2018 ADA Standards of Medical Care in Diabetes.

The proposed research has great potential to enhance evidence quality, empowering disadvantaged patients with T2D to make informed health decisions and improve outcomes. The study is designed to iteratively tailor DTM to the specific needs of the H/L patients, caregivers, and providers. It addresses several access issues consistently identified in disparities research and has the potential to improve adherence through increased engagement. |

#### 4. OBJECTIVE(S)/SPECIFIC AIMS AND HYPOTHESES

- *A concise statement of the goal(s) of the current study.*
- *The rationale for and specific objectives of the study.*
- *The goals and the hypothesis to be tested should be stated.*

**Objectives:**

Diabetes Telehealth Management (DTM) improves important outcomes, such as glycemic management (GM) and quality of life (QoL). It is yet unknown whether these results generalize to Hispanic/Latino (H/L) disadvantaged populations with Type 2 Diabetes (T2D), primarily when utilizing community-based participatory research (CBPR) approaches involving patients, caregivers, providers and other stakeholders in the process of adapting the intervention. Our goal is to compare DTM to comprehensive outpatient management (COM) on critical patient-centered outcomes. Both are based on 2018 American Diabetes Association (ADA) guidelines. We propose a multiphase mixed method, CER RCT to:

**Specific Aim 1: Assess usability of an evidence-based DTM intervention utilizing a CBPR approach and adapt it to facilitate acceptability and feasibility in a population of H/L patients with T2D, and their caregivers and providers.**

**Specific Aim 2: Assess whether H/L patients receiving DTM attain significantly *improved* patient-centered outcomes compared to COM, through a CER RCT. *Expected outcomes* include *improved* diabetes QoL, GM, blood pressure (BP), cholesterol, medication adherence, and diabetes self-efficacy (SE), and *reduced* diabetes distress, problem areas in diabetes (PAID), inpatient utilization, unscheduled T2D physician visits and sick days.**

**5. RESOURCES AVAILABLE TO CONDUCT THE HUMAN RESEARCH**

- *Explain the feasibility of meeting recruitment goals of this project and demonstrate a potential for recruiting the required number of suitable subjects within the agreed recruitment period*
  - *How many potential subjects do you have access to?*
- *Describe your process to ensure that all persons assisting with the trial are adequately informed about the protocol and their trial related duties and functions*

The specific population affected by the research is underserved T2D patients. Our estimated sample size is 200 patients (240, assuming a 10% attrition rate). We propose to study H/L patients with T2D, recruited from the Ambulatory Care Unit at LIJMC and the Division of General Internal Medicine Practice located in Queens NY, one of the most diverse populations in the world. We also propose to recruit at Southside Hospital. NUMC and Glen Cove Hospital as well as the Dolan Family

Health Center. We selected these sites because 1) clinic patient statistics meet our enrollment criteria, with 4,092 adults H/L patients with T2D (well over the 200 recruitment number required). 2) clinicians at these sites express enthusiasm for/commitment to the study and what it might mean for their H/L patients with T2D. These sites provide a real-world setting for implementation because LIJMC is where our target population of H/L disparity patients with T2D (many with limited English proficiency) receive their care (H/Ls comprise 27.5% of Queens' population).

Staff have all reviewed and been trained on methods for the study outlined in the protocol. There will be an initial kick off meeting to discuss the protocol in further detail. They have all completed CITI training and compliance for HIPPA data. |

## 6. RECRUITMENT METHODS

- *Describe the source of potential subjects*
- *Describe the methods that will be used to identify potential subjects*
- *Describe any materials that will be used to recruit subjects. A copy of any advertisements (flyers, radio scripts, etc.) should be submitted along with the protocol.*
- *If monetary compensation is to be offered, this should be indicated in the protocol*

To limit selection bias, and ensure true random selection, our Biostatistics Unit will randomly (using a random number generator) sample 400 patients from the 4,092 total patients.

**Recruitment:** The bilingual study RN, Multisite Patient Engagement Specialist or study coordinator will be responsible for recruitment at the various study sites. Given COVID-19 pandemic we will also be calling be patient over the phone to recruitment.

**Recruitment for Data Collection:** Eligible patients will be approached and called for consent (consent form 1) to have longitudinal data collected, including surveys at specified time points over the 12 months of their participation. Patients who are called will be give verbal consent. Next, bilingual study RN, Multisite Patient Engagement Specialist or study coordinator will obtain the randomization number from the Biostatistics Unit for the patient to determine if they were allocated to the DTM arm or COM arm. If the patient is randomized into the DTM arm, the recruiter will approach to obtain a second consent (consent form 2) to receive DTM. Verbal consent will be given for patients who are called for recruitment.

Informed consent will include a detailed but simple description, in patient's preferred language, of study risks/benefits.

**Recruitment for DTM:** Eligible patients will be approached or called for consent (consent 1) to have longitudinal data collected, including surveys at specified time

points over the 12 months from signing consent, in order to determine health outcomes. Next, the research coordinator will obtain the randomization number for the patient to determine if they were allocated to the DTM arm or COM arm. If the patient is randomized into the DTM arm, the coordinator will approach to obtain a second consent (consent 2) to receive DTM.

Informed consent for DTM will include a detailed description, in English and Spanish, of the risks and benefits of the study with user-friendly images of the equipment. If the patients decline to participate in DTM, they will continue to receive standard of care and still have surveys administered and data collected over time (as agreed to in consent 1). Based on intention to treat (ITT), they nevertheless will be analyzed as part of the DTM group.

For those patients randomized to DTM, the RN will explain to the patients that if they agree to participate, they will be asked to measure vital signs daily, receive weekly telehealth “visits” with the telehealth RN (with appropriate assurances regarding confidentiality), and receive reminders of their weekly visits. The experienced bilingual RN will be trained in the proper recruitment of patients to eliminate selection bias based on a standardized protocol. The research RN will also explain to the DTM patient that s/he will have a bilingual trainer meet them at their home and that they will receive training on how to properly use the equipment.

For those patients randomized to COM, the research RN will have monthly phone contacts to determine how the patient is doing, how many days during the week they have been sick, and whether they have been to an unscheduled doctors visit, the ED or hospital during the last month and how many days they have been sick. Lastly, in both groups, the enroller will let patients know that they will be asked to complete pre and post surveys. The enroller will be trained on the proposed enrollment practices to ensure objective, unbiased and systematic selection and recruitment of participants.

DTM patients will be asked if they prefer to involve their caregiver; if patients agree, caregivers will be provided with the caregiver app (Figure 3). The bilingual enroller will explain to DTM patients that they will provide DTM training at their home.

We propose to study H/L patients with T2D, recruited from the Ambulatory Care Unit at LIJMC and the Division of General Internal Medicine Practice located in Queens NY, one of the most diverse populations in the world. We also propose to recruit at Southside Hospital. NUMC and Glen Cove Hospital as well as the Dolan Family Health Center. We selected these sites because 1) clinic patient statistics meet our enrollment criteria, with 4,092 adults H/L patients with T2D (well over the

200 recruitment number required). 2) clinicians at these sites express enthusiasm for/commitment to the study and what it might mean for their H/L patients with T2D. These sites provide a real-world setting for implementation because LIJMC is where our target population of H/L disparity patients with T2D (many with limited English proficiency) receive their care (H/Ls comprise 27.5% of Queens' population).

Due to COVID-19 pandemic, we are also requesting patients be enrolled into the study via telephone by providing us with verbal consent. Surveys and questionnaires will be performed over the phone in the preferred language of the participant.

For patients reaching 6 month or 12 month follow-up during this time, interviews and surveys/questionnaires will also be collected over the phone.

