### INCLUSION AND EXCLUSION CRITERIA

**Inclusion criteria:** 1) H/L patients with a diagnosis of T2D alone or in combination with other chronic conditions (e.g., heart disease); 2) age > 18 speak English or Spanish.

Caregivers age >18 taking care of a patient with T2D alone or in combination with other chronic conditions.

Providers who treat patients with T2D alone or in a combination with other chronic conditions

**Exclusion criteria:** 1) patient is not a H/L with a diagnosis of T2D; 2) age <18.  
Identification of study participants: There are 4,092 H/L patients with T2D fitting our inclusion criteria.  
Caregivers age <18 who do not take care of a patient with T2D or in combination with other chronic conditions  
Providers who do not treat patients with T2D alone or in a combination with other chronic conditions.

Our goal is to enroll 224 (240, assuming a 10% attrition rate) patients/20-months. With a 50% acceptance rate (estimated on our previous enrollment experience), we will need to approach 400 total patients (or 20/month) to enroll 12 patients per month, easily reaching our goal of 224 participants over the 20-month accrual period.

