## 8. NUMBER OF SUBJECTS

- *Indicate the total number of subjects to be accrued locally. If applicable, distinguish between the number of subjects who are expected to be pre-screened, enrolled (consent obtained), randomized and complete the research procedures.*
- *If your study includes different cohorts, include the total number of subjects in each cohort.*
- *If this is multisite study, include total number of subjects across all sites.*

For the pilot test in Aim 1, we will have 12 subjects. For the RCT in Aim 2, we will randomize 224 patients. We plan to consent 224 patients assuming there will be a 10% attrition rate.

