**1b. Quantitative approach.** This adaptation phase involves an ongoing formative process evaluation of usability using quantitative methods so that adjustments can be made as DTM is implemented. Below is how we will operationalize usability measures. **The first two usability variables will be collected upon subject enrollment in the RCT:**

**1bi. Rate of acceptability.** To simulate the rate of DTM acceptability in the real outpatient environment, we propose to determine, among those who DO NOT consent to be part of the study, the proportion who state that their reason is related to the technology (as opposed to those who simply do not want to be part of a study). This will allow us to compute the “acceptability rate” (as opposed to “acceptance rate” below). Data from other studies most similar to the intervention proposed herein indicate that telehealth acceptability in a general population may be as high as 96%. As acceptability may be different for the H/L disparity population, it is important to measure. Assuming the probability of acceptability in disparity populations is significantly lower (50% rather than 96%) and a total of 200 (240, assuming a 10% attrition rate) patients will need to be randomized (100 per arm) then, approximately 400 patients will need to be approached to yield 200 who consent to enroll. The actual acceptability rate will be calculated as  $X/200$ . Assuming the rate=50% and  $n=200$ , acceptability rate can be estimated to within +/- 7.1% using (95% CI for proportions).

**1bii. Rate of equipment acceptance:** Of those randomized to DTM, the rate of “acceptance” will be the % of patients who accept the app and peripherals. We will randomize 200 patients (240, assuming a 10% attrition rate), to yield a maximum of 100 patients per arm/3 years, the maximum number that can be treated with DTM over 6 months. Assuming 90% of DTM patients will constitute the usability sample, DTM acceptance is estimated +/- 6% (95% CI for proportions). ITT analysis will include all patients randomized to DTM. **The following usability variables will be collected during and upon completion of RCT:**

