	Pilot												Pilot Patient/Caregiver Focus Groups (2)												Pilot Analysis												PAC Focus Group: Post-Pilot Adaptions												Provider Focus Group: Post-Pilot Adaptions												CAB Finalizes Intervention Adaption												Analysis													
Interventions	CAB												PAC												CAB												Pilot Study												Pilot Focus Groups												PAC												CAB												CAB/BPAC	
	6 MONTH FOLLOW UP												12 MONTH FOLLOW UP												12												12												12												12												12													
Study Aims	Specific Aim 1: Assess usability of an evidence-based DTM intervention utilizing a community based participatory research approach and adapt it to facilitate acceptability and feasibility in a population of Hispanic/Latino patients with T2D, and their caregivers and providers.																																										Specific Aim 2: Assess whether Hispanic/Latino patients receiving DTM attain significantly improved patient-centered outcomes compared to COM, through a CER RCT. Expected outcomes include: improved diabetes quality of life, glycemic management, blood pressure, cholesterol, medication adherence, and diabetes self-efficacy, and reduced diabetes distress, problem areas in diabetes, inpatient utilization, unscheduled T2D physician visits and sick days.																																											

1. Estimated number of potentially eligible participants (describe how number was determined [e.g., Electronic Health Record, claims data, clinic logs, administrative data, other]):	4092
2. Total number of study participants expected to be screened:	400
3. Total number of study participants expected to be eligible of those screened:	400
4. Target sample size (use same number stated in milestones):	200
5. If applicable, total number of practices or centers that will enroll participants:	2
6. Projected month first participant enrolled (month after project initiation):	1/2019
7. Projected month last participant enrolled (month after project initiation):	12/2021
8. Projected rate of enrollment (anticipated number enrolled per month of enrollment period):	8 to 10
9. Estimated percentage of participant dropout:	10%

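### At the stated 50% acceptance, approaching 400 patients is expected to enrol 200, not the 224 (12 per month) that the plan derives from it

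*Combined protocol and SAP*

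**What the plan says.** Section 6 (Recruitment Methods) sets the draw. To limit selection bias, the Biostatistics Unit will use a random number generator to "sample 400 patients from the 4,092 total patients".

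Section 7 (Inclusion and Exclusion Criteria) links the draw to the target. The goal is "Our goal is to enroll 224 (240, assuming a 10% attrition rate) patients/20-months". Taking 50% acceptance from previous enrolment experience, it continues "we will need to approach 400 total patients (or 20/month) to enroll 12 patients per month", and concludes that this means "easily reaching our goal of 224 participants over the 20-month accrual period".

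Section 8 (Number of Subjects) repeats the target: "For the RCT in Aim 2, we will randomize 224 patients". Section Five (Sample Size Justification) gives 224, or 112 per group.

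Other places work to 200. Section 12, item 1bi, uses the same 400 and the same 50% and states that "approximately 400 patients will need to be approached to yield 200 who consent to enroll". Sections 5 and 6 call 200 the number required. The recruitment table after Figure 4 lists 400 screened, 400 eligible, a target of 200, enrolment of 8 to 10 per month, first enrolment in 1/2019 and last in 12/2021.

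The documents describe no reserve list and no further draw.

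**The concern.** Four figures in one statement of Section 7 (50% acceptance, 400 approached at 20 per month, 12 enrolled per month, 224 in 20 months) cannot all be true. The first two give a smaller enrolment than the last two. Section 12 reaches the smaller figure from the same inputs.

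This has practical effect because Section 6 turns 400 into an instruction to the Biostatistics Unit. If the list is used up at about 200 enrolled, the trial either closes below the size on which its power statement rests or extends the list in a way that the plan does not describe. Section 6 chose random sampling to avoid selective recruitment, so an extension that is not random would weaken that safeguard.

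**Working it through.** **Inputs.** Names drawn and approached: 400 (Sections 6 and 7). Acceptance: 50% (Section 7). Contact rate: 20 per month for 20 months (Section 7). Target: 224, or 240 with the stated attrition allowance (Sections 7 and Five). Difference 0.45%, SD of change 1.2%, two-sided alpha 0.05, 112 per group (Section Five). Dropout: 10% (recruitment table).

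**Reproducing the plan's own yields.** Expected enrolment = number approached × acceptance.

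- Section 12: 400 × 0.50 = 200. This reproduces.
- Section 7, monthly: 20 × 0.50 = 10, against 12 stated. This does not reproduce.
- Section 7, total: 10 × 20 = 200, against 224 stated. This does not reproduce.
- The stated 12 per month over 20 months is 12 × 20 = 240, so it does not match 224 either.

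**Acceptance that the stated results would need.** 224/400 = 56%. 12/20 = 60%, which equals 240/400.

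**Shortfall.** 224 − 200 = 24, and 24/224 = 10.7%. Against 240: 240 − 200 = 40, and 40/240 = 16.7%.

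**Chance of reaching the target from 400.** If each patient accepts independently with probability 0.5, enrolment is Binomial(400, 0.5). P(at least 224) = 0.0093, and P(at least 240) = 0.00004.

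**Effect on power.** Two-sample t-test, standardised difference 0.45/1.2 = 0.375.

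| Situation | Per arm | Power at 0.45% |
|---|---|---|
| 224 randomised, all analysed | 112 | 79.8% |
| 200 randomised, all analysed | 100 | 75.1% |
| 224 randomised, 10% without data | 112 × 0.9 = 100.8 | about 75.5% |
| 200 randomised, 10% without data | 100 × 0.9 = 90 | 70.6% |

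The first row reproduces the stated 80% power for 112 per group. Comparing like with like, the recruitment shortfall costs 79.8 − 75.1 = 4.7 points before attrition and 75.5 − 70.6 = 4.9 points after it. The rest of the distance from 80% down to 70.6% is attrition that the 224 does not absorb, which is a separate matter.

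Section Five also attaches 80% power to a 0.5% difference (0.5/1.2 = 0.417). There, power is 87.4% at 112 per arm, 83.5% at 100 and 79.4% at 90.

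**Names needed.** Target/0.50: 224/0.50 = 448, or 448/20 = 22.4 contacts per month. 240/0.50 = 480, or 24 per month.

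**The case against.** The strongest reply is that this is a slip in planning figures with an easy remedy. The 50% is an estimate, and 56% acceptance would deliver 224. The pool of 4,092 leaves 4,092 − 400 = 3,692 patients from whom the same unit could draw again at random. If the true target is 200, the draw of 400 is exactly right. At a 0.5% difference, 200 randomised with 10% lost still gives 79.4% power. The 90-per-arm figures also assume that dropouts contribute nothing, whereas Section 12 plans to keep collecting outcomes after discontinuation and to use multiple imputation.

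Most of this stands, and it limits the point. It does not reconcile Section 7, which derives 224 from 400 at 50%.

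A reader might infer four stronger things that the documents do not support.

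- That the trial cannot reach 224. It is only not expected to at the assumed 50%.
- That the sample is drawn once, so that any extension must be ad hoc. The text does not say so; it is silent on further draws. Treatment allocation follows the first consent, so a non-random extension would affect who is invited, not the comparison between arms.
- That the table's 8 to 10 per month confirms a yield of only 160 to 200. That pairs the table's rate with Section 7's 20 months. The table's own window of 1/2019 to 12/2021 is about 36 months, which gives 8 × 36 = 288 to 10 × 36 = 360. What needs reconciling there is the two accrual windows.
- That the recruitment error alone takes power from 80% to 70.6%. About half of that fall is unabsorbed attrition.

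It is plausible that 400 was left over when 224 replaced 200, but no amendment history is shown, so this remains an inference.

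**Conclusion.** The concern holds as an internal contradiction in the recruitment figures. Under the plan's own 50% assumption, 400 approached is expected to give 200 enrolled at 10 per month, which is 24 (10.7%) below 224, with about a 0.9% chance of reaching 224. That probability rests on independent acceptances at exactly 50%; a higher acceptance rate would change it. The cost in power for 0.45% is about 5 points, whether or not 10% attrition is counted. It rests on the stated SD of 1.2% and a simple t-test, and the post-attrition figures further assume that patients who drop out add no information. The size of the source population is not a limit. The underlying fault is that 200 and 224 both stand as the target.

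**What to change.** 1. Settle one enrolment target and state it in Sections 5, 6, 7, 8 and 12 (items 1bi and 1bii), in Section Five, and in Figure 4 and its table.
2. Derive the draw and the rates from that target. At 50% acceptance over 20 months:
   - Target 224: 448 names, about 23 contacts and 224/20 = 11.2 enrolled per month.
   - Target 240: 480 names, 24 contacts and 12 enrolled per month.
   - Target 200: the 400 stands, and the 12 per month and 224 in Section 7 are corrected.
3. Reconcile the recruitment table's screened number, target, monthly rate and 1/2019 to 12/2021 window with the 20-month accrual period.
4. Since 448 or 480 names reach the target only on average, have the Biostatistics Unit generate the list in random order and release names in that order. State in Section 6 that any extension continues down the same list.

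The cost is 448 − 400 = 48 to 480 − 400 = 80 more recruitment contacts, from a list already held, and edits to the text. If 200 is kept, only the text changes.
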